
Intervention: Aim 3:
 
Primary Outcome: CRC screening status at 3 months (>60%)
 
Secondary Outcomes:
 
• Intention to screen at 2 weeks (>80%)• Enrollment (target of n=30)• Maintain a retention rate (completion of baseline, 2 and 12 week surveys) >65% at 12 weeks• Viewing videos (# views, # repeat views)• Completion of baseline and follow up questionnaires (retention)• Responding to request to contact clinic/navigation services• Sharing any content with social network

Locations/Facilities
 
Surveys will be completed online
 
Recruitment for surveys will take place in-person, using social media, flyers in public spaces
 
Intervention: Aim 3: Recruitment will take place with flyers, word or mouth and presentations to introduce the study at partner and CAB member places of business and worship. These include community health clinics, local gyms, barbershops, stores, churches. We will use social media, newsletters and text messaging avenues of communication as utilized by our community and clinic partners. We will also use radio announcements on local health focused radio shows.

1 - Background/Literature Review

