4.2 Number of Participants

We require 8-10 men for the Community Advisory Board and we require n=175 Black or African American for survey in PART1. The intervention component will require n=30 men

Total study n=225

The survey component was powered on the interaction term "discrimination*preventive care engagement", both continuous, using a simulation study of 1000 runs of a logistic regression model, with the binary screening behavior response (1 = screened, 0 = not screened). A sample size of 175 subjects generates 80% power to detect a "small to moderate" effect size of 0.38 (corresponding odds ratio = 2.01, using R package "effect size") for the interaction term (continuous*continuous), at 5% level of significance, using a one-sided Z-test. To account for individuals who start but do not complete the survey we have added a buffer of 20% which gives a sample size of n=210 for the survey. The sample size has been chosen for the intervention to support an initial examination of intervention effectiveness using a one-arm design. This is a typical size that will generate pilot data on the feasibility of our approach.

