4.4 Recruitment Procedures

Recruitment Procedures Survey:

Recruitment will use a multipronged approach including community advertising, social media, word of mouth and leveraging of our community partners.

1.) Onsite at barbershops, Health Living and Learning Center (HLLC) and other community partner sites: Supervised by the research team, graduate and undergraduate students will be introduced to community partners and trained to introduce the study to potential participants who visit partnership businesses and organizations across the City of Petersburg. Project personnel will have a regular, weekly presence at each community partner site to build recognition and recruit to the survey.

- 2.) Additional recruitment pathways include distribution of study advertisements. These will be posted physically at various community locations and include a URL and QR code that enable access to the survey. We will also leave study information postcards (same URL and QR code) for distribution by community partners. We will also ask community partners with email lists, regular newsletters and other similar distribution lists to send out information about the study on their listservs.
- 3.) Social Media: distribution of study and survey advertising (including a link to the survey) using various social media platforms(e.g., direct recruitment via Facebook ads, posting information on VCU, VSU, and community partner social media accounts).
- 4.) Referral of friends (snowball) participants who complete the survey will have the option of completing a quick and seamless electronic recommendation for friends or family to consider participating.
- 5) Clinic partners. We have partnered with CVHS which has 4 clinics in the Petersburg city and surrounding counties. We will advertise in the clinic waiting rooms, staff at the clinics will hand out flyers for the study, and we will use any newsletters distributed by the clinic including playing our video on the television in the waiting rooms and sending invites to learn more via the text messaging system the clinic uses to distribute public health information, updates and health messages.

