6.1 Sample Size

The survey component was powered on the interaction term "discrimination*preventive care engagement", both continuous, using a simulation study of 1000 runs of a logistic regression model, with the binary screening behavior response (1 = screened, 0 = not screened). A sample size of 175 subjects generates 80% power to detect a "small to moderate" effect size of 0.38 (corresponding odds ratio = 2.01, using R package "effect size") for the interaction term (continuous*continuous), at 5% level of significance, using a one-sided Z-test. To account for individuals who start but do not complete the survey we have added a buffer of 20% which gives a sample size of n=210 for the survey.

We will also conduct focus groups with n=16 men.

Total project sample size n=226

Intervention Sample Size: To perform an initial test of efficacy, satisfaction and feasibility, we will test the intervention on 30 men.

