6.2 Intervention Planned Analyses

Analysis. All variables will be described using standard methods for continuous and discrete variables and examined for completeness. An interaction effect of discrimination and engagement in preventive care will be assessed, controlling for other confounders, using a logistic regression model with the binary

response (cancer screening). Additional analysis will be conducted, controlling for demographics, via a random intercept logistic regression model. Parameter significance will be determined at the 5% level.

Research measures collected at baseline, exit and 12 weeks post are: CRC knowledge, risk perception, medical mistrust, preventive health behaviors. At 12 week only, CRC screening or intent to screen, and participant satisfaction with the intervention will be asked. Process evaluation will assess any change in CRC knowledge, risk perception, medical mistrust, and preventive health behaviors at 12 weeks.

Feasibility will be assessed using a priori benchmarks for recruitment and retention. The recruitment benchmark will be consenting 100% of the recruitment goal. Acceptance rates and reasons for declining participation will be tracked. Information on refusals will be used to modify recruitment methods as needed. Retention benchmarks will be supported if $\geq 65\%$ complete both weeks 2 and 12 follow up. Engagement benchmarks will be supported if $\geq 65\%$ of intervention completers who do not have a primary care provider chose to receive navigation services; 80% of those consented view intervention materials (e.g., click on text/graphical data, view videos, complete risk assessment).

Preliminary Efficacy. A signal for efficacy will be considered positive if among those who complete the intervention a) most ($\geq 60\%$) complete CRC screening and b) $> 80\%$ acknowledge their intent to get screened.

Follow-up interviews. Interviews will be conducted with all participants to collect in-depth, descriptive feedback on satisfaction with the intervention content, delivery modalities, ease of use and usefulness. We will also interview clinic staff and Community Champions to gain insight into facilitators and barriers to recruitment efforts and response of the community to the intervention. Suggestions for additions and alterations will be solicited from all interviews.

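### The 65% navigation benchmark counts only men who complete the intervention, which leaves out logged choices of men who drop out, tends to overstate uptake and shrinks an already small denominator

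*Combined protocol and SAP*

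**What the plan says.** Section 6.2 (Intervention Planned Analyses) introduces two criteria with "Engagement benchmarks will be supported if". The first requires at least 65% "of intervention completers who do not have a primary care provider chose to receive navigation services". The second, in the same sentence, requires that "80% of those consented view intervention materials". The first is restricted by completion and by provider status; the second is restricted by neither.

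Other sections bear on the first criterion:

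- **Sample size.** Section 6.1 says "we will test the intervention on 30 men". Section 4.2 justifies the number with "This is a typical size that will generate pilot data on the feasibility of our approach". Neither gives an expected number of men without a provider.
- **Who can request navigation.** Under section 5.4 the request link opens to every enrolled man once he has finished the baseline questionnaire, whatever his provider status.
- **What is recorded.** The Synopsis, section 5.3 and section 5.8 all list "Responding to request to contact clinic/navigation services" with no subgroup limit. Section 5.8 places it among the user engagement data collected by the app.
- **Provider status.** The nearest variable is a single item on regular source of primary care (section 5.8), asked at baseline only (Table 2).
- **Completion.** The plan does not define an intervention completer. The nearest concept is retention, for which the Synopsis outcome list has "Maintain a retention rate (completion of baseline, 2 and 12 week surveys) >65% at 12 weeks". Hypothesis H3 in the Synopsis sets more than 75%, and section 6.2 sets at least 65%.

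**The concern.** Of the two restrictions, provider status is a baseline characteristic and a legitimate way to define a target group. Completion is different, because it is known only after the man has had the chance to engage or not. Conditioning on it selects on something likely to be related to the outcome: a man who loses interest is less likely both to ask for a navigator and to finish the surveys. His non-request is then dropped rather than counted as a failure. A man who asks for navigation in the first week but misses the 12-week survey is also dropped, and his success is lost. On balance the first kind of loss seems more likely, so the observed percentage tends to be too high.

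The restriction also costs precision. The target group is a fraction of 30 men, and removing dropouts makes it smaller still. No interval or minimum denominator is attached, so the result is a bare pass or fail. At stake is one of the feasibility conclusions of the pilot: whether men without a provider take up navigation at a rate that supports the approach.

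**Working it through.** **Figure to reproduce.** There is none. The plan gives no power, precision or expected denominator for this benchmark.

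**Inputs from the documents.** Sample of 30 (section 6.1). Threshold 65% (section 6.2). The retention targets stand in for completion: more than 65% of 30 is more than 19.5, so 20 men; more than 75% of 30 is more than 22.5, so 23 men.

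**Assumption.** The share of men without a provider is taken as 20% to 40%. The documents give no figure.

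**Step 1, size of the denominator.** Expected m = completers × share.

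- Lowest: 20 × 0.20 = 4.0
- Highest: 23 × 0.40 = 9.2

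So about 4 to 9 men.

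**Step 2, what the rule does at that size.** The number needed is k = 65% of m, rounded up. The chance of passing is P(X ≥ k) with X ~ Binomial(m, true uptake). The last column is the exact (Clopper-Pearson) interval at a bare pass.

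| m | k needed | effective bar | passes if true uptake is 50% | passes if true uptake is 80% | 95% interval for k/m |
|---|---|---|---|---|---|
| 4 | 3 | 75% | 31% | 82% | 19% to 99% |
| 5 | 4 | 80% | 19% | 74% | 28% to 99% |
| 6 | 4 | 67% | 34% | 90% | 22% to 96% |
| 8 | 6 | 75% | 15% | 80% | 35% to 97% |
| 9 | 6 | 67% | 25% | 91% | 30% to 93% |
| 12 | 8 | 67% | 19% | 93% | 35% to 90% |

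For m = 4 to 6, a true 50% passes 19% to 34% of the time. A true 80% fails 10% (100 − 90) to 26% (100 − 74) of the time. Rounding alone moves the effective bar between 67% and 80%.

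**Step 3, effect of the completion condition.** The documents give no figure for the difference in uptake between completers and dropouts, so this is an illustration only. Take 9 consented men without a provider (30% of 30), of whom 6 complete. Suppose 4 of the 6 completers and 1 of the 3 dropouts request navigation.

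- As written: 4/6 = 67%, which passes.
- Without the completion condition: (4 + 1)/(6 + 3) = 5/9 = 56%, which fails, because 9 men need 6.

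The recorded choices are the same and the verdict is the opposite.

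**Step 4, denominator after removing the completion condition.** Expected m = 30 × 0.20 = 6 to 30 × 0.40 = 12. Allowing m to vary binomially, given at least one eligible man:

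| Share without a provider | Base | true 50% passes | true 80% passes |
|---|---|---|---|
| 20% | 20 completers | 33% | 81% |
| 20% | 30 consented | 27% | 83% |
| 40% | 20 completers | 22% | 85% |
| 40% | 30 consented | 15% | 89% |

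The gain in discrimination is modest. The main gain is that the selection on completion is removed. Because precision stays low, the count and interval are needed in either case.

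**The case against.** The strongest reply is that the benchmark is a deliberate choice for a pilot. Men without a provider plausibly need navigation most, and counting everyone would treat a man who arranges screening through his own provider as a failure. Navigation appears in none of H1 to H3, no stop or go decision hangs on this benchmark, and 30 is offered as a pilot size. All of this stands. It defends the provider restriction and keeps the consequence modest, but it gives no reason for the completion restriction.

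The reply also limits what may be concluded. Four stronger readings are tempting:

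- **That the denominator could well be empty.** With a 20% share and 20 completers the chance of no eligible man is 0.80^20, about 1%. It reaches 9% to 12% only if the share is about 10%, and the documents do not say so.
- **That clinic recruitment makes the group smaller.** Section 4.4 does say "We have partnered with CVHS which has 4 clinics in the Petersburg city and surrounding counties", but clinics are one route among many. The poverty described in section 1.1 and the enrolment of men due for screening could push the share the other way.
- **That pass or fail is close to chance.** A pass rate near one half at a true uptake of exactly 65% is a property of any threshold: with all 30 men, needing 20, it is 51%. Away from the threshold, 8 or 9 men give 15% to 25% at a true 50% and 80% to 91% at a true 80%. That is weak but not random.
- **That the study ignores requests from other men.** Navigation response is a secondary outcome with no subgroup limit, and section 6.2 says all variables will be described. Those requests are left out of this one threshold only.

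**Conclusion.** The point holds for the completion condition. Section 6.2 makes the navigation benchmark depend on a post-enrolment event, although the choices of men who leave are recorded, and the neighbouring viewing benchmark avoids this. The likely direction is overstatement, provided men who complete are more engaged than men who do not. The amount cannot be estimated from the documents.

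The size of the denominator rests on two assumptions: that 20% to 40% of men lack a provider, and that completion follows the retention targets. On those, about 4 to 9 men decide the result, with the misclassification rates shown for 4 to 6 men at the lower end of that range. If the share is higher, the precision problem eases but the selection problem remains.

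A reader might infer that restricting the benchmark to men without a provider is itself an error, or contradicts the listed outcome. The documents do not support that: the outcome lists state no denominator, and a threshold for a target subgroup can sit beside a wider descriptive outcome. This should be corrected, but it concerns a secondary feasibility conclusion and does not touch the primary outcome.

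**What to change.** In section 6.2:

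1. Define the benchmark denominator as all consented men who report no regular source of primary care on the existing baseline item, whether or not they complete follow-up.
2. Count a man in that group who makes no navigation request as not choosing navigation.
3. Report the count and denominator with an exact 95% interval beside the pass or fail result.
4. Report alongside it the number requesting navigation among all consented men, also with an exact 95% interval and with no threshold.
5. State how many consented men never finish the baseline questionnaire. They cannot be classified by provider status and the request link does not open for them, so they enter item 4 as non-requesters but cannot enter item 1.

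The cost is a short edit to section 6.2. The baseline item and the app records are already planned, so no new data are needed. The downside is that the observed percentage may be slightly lower than among completers. The interval will still be wide: a bare pass of 8/12 runs from 35% to 90%. Whether to keep the no-provider group as the target is for the team to decide.

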[figure not shown]

CLINICAL STUDY PROTOCOL

MCC-21-18632

SUCCEED: Engaging Black Men in CRC Screening

NCT05980182

9/08/2021

SUCCEED: Engaging Black Men in CRC Screening

Protocol Number

HM20023619

Principal Investigators

[name] (VCU)

[name] (VSU)

Protocol Version

8 September 2021

VCU Study Personnel

Principal Investigator	[name] Email: [contact]
Co-Investigator	
Research Assistant	
Student/RA	

Synopsis

Purpose

To determine the unmet needs, attitudes, barriers and facilitators of AA/Black men use of colorectal cancer screening and describe how community leaders such as barbers may act as Community Champions to educate and facilitate screening participation.

Objectives

Aim 1. Determine factors associated with self-reported CRC screening behaviors among (n=175) AA/Black men in Petersburg, VA.

Aim 2. Develop tailored S2S content for AA/Black men to be delivered using a combination of short video and text-based information optimized for delivery via QR codes for smartphones.

Aim 3. Test intervention on a sample of n=30 AA/Black men who are due for CRC screening. The primary aim is: completed CRC screening (any type) at 3months. Secondary aims are:

to collect process data to assess satisfaction and feasibility.

H1. Preliminary effectiveness of the intervention will be shown with >60% of men enrolled obtaining a CRC screen (any modality) by 12 weeks

H2. At Week 2 >80% of men enrolled will endorse an intention to be screened

H3. We will be able to recruit a sample of n=30 men into the intervention and maintain a retention rate (completion of baseline, 2 and 12 week surveys) >75%

Study Population

Survey Eligibility Criteria: Men aged 45-75 who reside in Petersburg and surrounding counties, and identify as AA/Black and have no personal history of cancer.

Intervention: For Aim 3 and additional criterion is that men have to be due for CRC screening upon study enrollment

Number of Participants

Survey: n=175

Intervention n=30

Study Design

Survey: Cross sectional; qualitative,

Intervention: single arm, pre-post Social behavioral intervention

Study Duration

Survey: 36 months total
 
Intervention: Aim 3: 12 months (once enrolled men are on study for three months)

Outcome Variables
 
Please see survey measures

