5.8 Data Collection Sources

Survey Measures. The survey has been designed to obtain key information while minimizing participant burden. *Demographics:* age, sex, highest attained education, annual household income, employment status, and marital status; health literacy (1 item); health status (1 item).

Medical Mistrust. measures (1) suspicion, (2) group (racial) disparities in health care, (3) lack of support from health care providers.

Perceived Racial Discrimination. Everyday Discrimination Scale reflect day-to-day experiences of unfair treatment. Higher scores corresponded to more frequent experiences of racial discrimination;

Preventive health care behaviors: The Good Health Practice Scale,⁶³ a 16-item scale that measures key preventive health behaviors. This scale has been shown to assess the avoidance of preventive health behaviors.

Social Support: MOS-SSS aims to assess the extent to which a person has the support of others to face stressful situations.

CRC Test fear and invasiveness and Cultural Attitudes about Masculinity: Males Role Norms Inventory-Short Form (MRNI-SF) is a 21-item questionnaire that assesses conformity to dominant cultural norms of masculinity (avoidance of femininity, negativity towards sexual minorities, self-reliance through mechanical skills, toughness, dominance, importance of sex, restrictive emotions). High total scores indicate greater conformity to traditional norms of masculinity

CRC Risk Perceptions. Lifetime risk of developing CRC will be asked on a 0-100% scale and a likert response adapted from the NIH HINTS.

Colorectal Cancer Screening Behaviors. Assessed using questions vetted by the national Behavioral Risk Factor Surveillance System we will measure those who have ever been screened and those who are up-to-date with screening

Focus Group: A focus group interview guide has been developed to inform how the barbers can be engaged to introduce the intervention, be empowered to have conversations about the need for CRC screening among Black men and encourage men to engage with the QR code and intervention materials.

Intervention.

1. Measures. See Table 2 above for all measures and timing of collection for the intervention.
 - a. Outcomes measures
 - i. CRC screening status (>60%) **OR**
 - ii. Intention to screen (>80%): from S2S
 - b. Covariates

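### The Aim 3 primary benchmark has two denominators, men enrolled in H1 and undefined completers in 6.2, so the same data can pass one and fail the other

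*Combined protocol and SAP*

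**What the plan says.** The Synopsis, under Objectives, states H1 as "Preliminary effectiveness of the intervention will be shown with >60% of men enrolled obtaining a CRC screen (any modality) by 12 weeks". H2 is a separate hypothesis: "At Week 2 >80% of men enrolled will endorse an intention to be screened". H3 aims to "maintain a retention rate (completion of baseline, 2 and 12 week surveys) >75" per cent. The Outcome Variables part of the Synopsis makes screening at 3 months (above 60%) primary and intention at 2 weeks (above 80%) secondary, and gives a retention target above 65%.

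Section 6.2, under Preliminary Efficacy, says: "A signal for efficacy will be considered positive if among those who complete the intervention" two conditions hold, (a) at least 60% screened and (b) more than 80% intending to be screened. No section defines who has completed the intervention. Within 6.2 itself, different benchmarks rest on intervention completers, on consented men, and on men who finish both follow-ups (at least 65%).

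Section 5.8 lists the outcome measures as "CRC screening status (>60%) OR" intention above 80%.

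On missing follow-up, 5.4 has men who have not answered the final survey within two weeks telephoned and offered phone, email or app completion, and 5.7 repeats this in brief. Section 6.6 refers missing data to standard procedures, in a paragraph about the REDCap survey.

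**The concern.** H1 and 6.2 both say when the pilot's screening result counts as encouraging, and they use different bases. Men who stay engaged may be more likely to be screened than men who drop out. A completer percentage can then exceed the enrolled percentage even though no more men were screened.

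Sections 4.2 and 6.1 set no null rate, significance level or precision for Aim 3, so this benchmark is the only stated test of the primary outcome. If two versions are available when the data arrive, the headline can depend on which one is chosen. No confirmatory decision rests on 30 men, but the result is meant to show whether the intervention looks effective.

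**Working it through.** The plan gives no calculation for Aim 3 to reproduce, so the check is to find the smallest passing count under each rule.

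**Inputs.** 30 men (6.1); more than 60% of men enrolled (H1); at least 60% screened and more than 80% intending among completers (6.2); retention at least 65% (6.2) or above 75% (H3). Assumption: a completer is a man who finishes the follow-up surveys. The documents do not say so.

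**1. H1.** 0.60 × 30 = 18. The count must exceed 18, so at least 19 of 30.

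**2. Number of completers.** 0.65 × 30 = 19.5, so at least 20. 0.75 × 30 = 22.5, so at least 23.

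**3. Section 6.2.** With m completers, (a) needs the smallest whole number not below 0.6m, and (b) the smallest whole number above 0.8m.

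| Completers m | 0.6m | Least screened (a) | Share of 30 enrolled if no other man was screened | 0.8m | Least intending (b) |
|---|---|---|---|---|---|
| 20 | 12 | 12 | 12/30 = 40% | 16 | 17 |
| 23 | 13.8 | 14 | 14/30 = 46.7% | 18.4 | 19 |
| 30 | 18 | 18 | 18/30 = 60% | 24 | 25 |

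The denominator does most of the work. With 20 completers, a strict inequality would raise (a) only from 12 to 13, against 19 under H1.

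**4. Where the rules disagree.**
- 20 completers: 12 to 18 screened meets (a). H1 fails at 12/30 to 18/30 if the other 10 men count as not screened, and is met at 22/30 to 28/30 if they count as screened.
- 23 completers: 14 to 18 screened meets (a). H1 fails at 14/30 to 18/30, or is met at 21/30 to 25/30 if the other 7 count as screened.
- The reverse also occurs: 9 to 11 of 20 (19 to 21 of 30 with the other 10 counted as screened), or 12 to 13 of 23 (19 to 20 of 30 with the other 7), fails (a) while H1 can be met.

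These ranges treat every non-completer's status as unknown. Table 2 in 5.4, as printed, also collects screening status at 2 weeks, so some lost men may already have reported a screen.

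**5. Chance of passing the screening part.** P(X ≥ k) for X ~ Binomial(n, p), at assumed true rates p. The same p is used for each rule and all 30 men are taken as observed under H1, so the table contains no selection effect.

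| Assumed p | 19 of 30 | 12 of 20 | 14 of 23 |
|---|---|---|---|
| 40% | 0.008 | 0.057 | 0.035 |
| 50% | 0.100 | 0.252 | 0.202 |
| 60% | 0.431 | 0.596 | 0.556 |

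**6. Inequality alone.** With all 30 men observed, only a count of exactly 18 meets (a) and fails H1. Its probability is 0.147 at an assumed true rate of 60%.

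**The case against.** The strongest defence is that H1 speaks of effectiveness in enrolled men and 6.2 of efficacy in completers, so they could be two deliberate quantities. The wording permits that, but no section says it, and 6.2 would still need a definition of completion. It is also true that this is a pilot of conventional size with no error rates set.

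Several stronger readings are tempting, and the documents do not support them:
- **That 5.8 is a third success rule, passed on intention alone.** The OR stands in a list of outcome measures and is not framed as a decision rule. It sits badly with the conjunction in 6.2 and with the primary and secondary split in the Synopsis, so it should be tidied, but no more can be read into it.
- **That the completer rule inflates the result by a known amount.** Upward bias is plausible, but its size cannot be derived, and step 4 shows the disagreement can run the other way.
- **That incomplete follow-up is ignored.** Sections 5.4 and 5.7 give contact steps. What is absent is a counting rule for men whose status is still unknown afterwards.
- **That the strict and non-strict inequalities matter much.** They differ only on an exact tie, such as 18/30 or 12/20.
- **That H2 has no data.** Table 2, as printed, marks intention at baseline and 12 weeks only, but the table may have been extracted wrongly. The conflict between H2 (Week 2) and the text of 6.2 (12 weeks only) stands without it.

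**Conclusion.** The point holds for the denominator. H1 needs 19 of 30. Section 6.2(a) can be met with 12 of 20 or 14 of 23, which is 40% or 47% of those enrolled if no other man was screened. With at least 17 of 20 or 19 of 23 stating intent, 6.2 as a whole is then positive while H1 fails. These figures rest on 30 men enrolling, on reading completion as finishing the follow-up surveys, and on retention at the plan's own benchmarks. Whether H1 truly fails depends on the unknown men, for whom there is no counting rule. The inequality, the OR in 5.8 and the timing of intention are secondary inconsistencies. This should be settled before the data are analysed.

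**What to change.** In 6.2, change the base of the efficacy signal from completers to all men enrolled, and make H1's threshold of more than 60% the single primary rule. That is 19 if 30 enrol. Recompute if fewer do, for example 17 of 28 (0.6 × 28 = 16.8) or 16 of 25 (0.6 × 25 = 15).

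Then add:
- Any screen reported at or before week 12 counts, including one reported at week 2. A man who reports a screen at week 2 and is then lost has already met H1's criterion.
- A man with no reported screen and no 12-week status counts as not screened in the primary figure. Show the opposite bound beside it, and say so if the conclusion differs.
- The completer proportion stays as a labelled sensitivity analysis, with completion defined in advance.
- Intention is reported separately as a secondary outcome on the enrolled denominator, once its timing agrees across H2, the Synopsis outcome list, 6.2 and Table 2.
- The OR in 5.8 is reworded to match.

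The cost is a few sentences and no new data. The downside is a stricter benchmark: if no lost man had already reported a screen, it needs 19 of 20 responders at 65% retention, or 19 of 23 at just over 75%. With substantial loss the two bounds will often disagree, and the report will have to say so. An exact 95% confidence interval (43.9% to 80.1% at 19/30) would be a useful addition but is not needed to remove the contradiction.
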